Evaluating the Hypotheses: Behavioral Analyses. We will evaluate the behavioral impact of the VOT and F0 acoustic dimensions on classification using *mixed-effects logistic regression* (with patient as a random effect, stimulus VOT and F0 as fixed effects and classification responses as the outcome). Following our prior work,^{14,25-29} perceptual weights for the dimensions will be computed for each patient as the correlation between dimension values and the proportion of *peach* classifications across all stimuli in the VOTxF0 stimulus grid with absolute values of the correlation coefficients normalized to sum to one as an *index of relative perceptual weight* in quiet (Aim 1) and in noise (Aim 2). To examine the impact of a change in 'accent' in the DBSL paradigm, we will use mixed logit models with responses as a function of patient, block, test stimulus F0 and the interaction between block and F0 (Aim 2). Patient will be modeled as a random effect, with the other factors as fixed effects.

Evaluating the Hypotheses: Neural Analyses. We will take a multi-pronged analysis approach. Our pilot data in **Figure 3** demonstrate that *high-y* activity (HGA) is modulated by graded acoustic details across the VOT and F0 dimensions across electrodes placed in the STP. Following the analysis pipeline used in our pilot data analyses, we will specifically examine stimulus-time-locked HGA to the *Test* stimuli, which possess consistent, perceptually-ambiguous VOT and differentiated F0. We have specific, directional predictions (detailed above)

regarding how HGA to F0-differentiated *Test* stimuli will vary according to perceptual weight in behavior. To briefly recap, we expect that HGA to *Test* stimuli will be better differentiated (1) in the Speech-in-Noise compared to the Clear baseline context (because F0 carries greater perceptual weight); (2) in the Canonical, compared to the Reverse, context; (3) in the Canonical, compared to the Baseline Clear Speech context (because stimulus statistics exaggerate the dimension regularity in behavior).

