High-gamma amplitude will be calculated using an approach that utilizes the Hilbert transform. Specifically, the signal will be filtered into 8 subbands, logarithmically spaced between 70-150 Hz. For each subband, we will calculate the amplitude (absolute value) of the analytic signal, which is estimated using the Hilbert transform. Each subband will be normalized to its baseline mean and standard deviation, estimated across trials. The HGA estimate is then the mean across these subbands.

We will use *least-squares linear regression neural encoding models* to investigate relationships between acoustic stimulus dimensions and STP neural responses during the baseline quiet context, in which stimuli sample a 2-d F0 x VOT grid. This approach will allow us to identify the subset of electrodes and temporal windows that encode at least one of these 2 dimensions at baseline; targeted analysis on this subset (described below) will then be used to compare listening contexts.

Encoding model inputs will consist of F0 and VOT, with an output of channel- and time-specific HGA. For a given electrode, individual models will be built using single trial data and a sliding window, allowing us to identify the temporal window relative to stimulus onset that yields significant models. Model quality will be assessed in two ways. First, using models built on all trials, we will calculate the regression *F*-statistic, which determines if any coefficients are significant. This will be compared to null distributions estimated with permutation tests that shuffle data across trials. Second, goodness-of-fit will be assessed for significant models by performing leave-one-out cross-validation and calculating R^2 , the proportion of variance in neural activity explained by the model. Finally, we will assess the relative encoding strength of each acoustic dimension using model coefficient *t*-statistics. In summary, this approach will allow us to identify the timing and anatomical location of F0 and VOT encoding during baseline quiet listening conditions for which dimensions are sampled orthogonally (as in **Figure 1a**).

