To characterize shifts in neural encoding across listening contexts, we will investigate Noise using encoding models and Canonical/Reverse contexts using *cluster-based approaches*.^{32,49} Encoding models will be built from the Noise context for all channels and timepoints, using the same approach as Baseline. If a channel/timepoint is significant in either Baseline or Noise, the F0 and VOT coefficient *t*-statistics will be compared across contexts. We hypothesize that encoding of F0 will strengthen and VOT will weaken in Noise, as measured by changes in *t*-statistic magnitudes across multiple models. Next, we will compare neural responses for each of the two *Test* stimuli (which were embedded in the F0 x VOT grids, **Figure 1a**) between Baseline vs. Canonical and Canonical vs. Reverse. The clustering approach will look only at Baseline significant channels and time windows and involves randomly assigning listening context labels to single-trial data followed by a *t*-test at each time step. Across all permutations, a criterion value will be established for each timepoint (>95% of absolute value of *t*). For each of these permutations, we will next determine whether its value exceeds criterion across timepoints, and for how many timepoints it exceeds criterion (a 'cluster'). For each cluster, *t* values will be summed and assigned to all points in the cluster, with the largest summed cluster value stored for each permutation. This will create a null distribution of 1000 cluster values. We then will establish whether the cluster size calculated across real neural data (organized according to listening context) exceeds the 95% permutation-based cluster values such that $p < .001$ indicates an observed cluster is greater than all permutation-based clusters. Using this approach, we will identify context-dependent shifts in HGA responses, which we predict will reflect observed shifts in perceptual weights. Namely, we hypothesize that HGA responses in F0-encoding channels will be enhanced in the Canonical context relative to both Baseline and the Reverse context.

Rigor and Reproducibility. Analyses will be controlled for multiple comparisons, with sex as a co-variate in our analyses. We will use pre-registration and provide access to all the deidentified source data.

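### The neural Canonical/Reverse cluster tests compare contexts within each Test stimulus, so they do not test the predicted change in F0 differentiation

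*SAP*

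**What the plan says.** All SAP references below are to Evaluating the Hypotheses: Neural Analyses unless another section is named.

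- **Prediction.** HGA to the Test stimuli, which share an ambiguous VOT and differ in F0, "will be better differentiated (1) in the Speech-in-Noise compared to the Clear baseline context (because F0 carries greater perceptual weight". The same sentence carries the prediction over to the other contexts: "2) in the Canonical, compared to the Reverse, context; (3) in the Canonical, compared to the Baseline Clear Speech context".
- **Planned test.** For the Canonical and Reverse contexts the SAP says "Next, we will compare neural responses for each of the two" Test stimuli, for Baseline against Canonical and for Canonical against Reverse. Context labels are shuffled over single trials, a t-test is run at each time step, and the largest summed cluster is compared with 1000 permuted values.
- **Prediction restated after the test.** "HGA responses in F0-encoding channels will be enhanced in the Canonical context relative to both Baseline and the Reverse context".
- **Channel selection.** The encoding models at baseline are used to "identify the subset of electrodes and temporal windows that encode at least one of these 2 dimensions at baseline". The Test stimuli belong to that baseline set, since the SAP describes them as stimuli "which were embedded in the F0 x VOT grids".
- **Normalisation.** "Each subband will be normalized to its baseline mean and standard deviation, estimated across trials". Whether this is done per block is not stated.
- **Behavioural counterpart** (Behavioral Analyses). The accent model takes "responses as a function of patient, block, test stimulus F0 and the interaction between block and F0".
- **Noise counterpart.** F0 and VOT coefficient t-statistics are compared between Noise and Baseline.
- **Order** (Protocol, Study Design, item 2). The clear-speech block comes first. Research Activities, item 1, describes a Canonical-Reverse block without saying how the two parts are arranged.

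**The concern.** Better differentiation is a statement about the gap between two stimuli and how that gap changes with context. The planned tests look at each stimulus separately and ask whether its response changes with context. F0 does not enter the statistic, and no rule says how the two results are to be combined. One significant and one non-significant result is not a test of their difference.

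A change in the evoked response that is common to both stimuli is therefore enough to produce clusters. For Baseline against Canonical, context is tied to order by design, so such a change is a live alternative explanation. For Canonical against Reverse the order cannot be judged from the Protocol. Per-block normalisation would remove slow drift, but not a change in the evoked response itself.

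At stake is whether a positive neural result can be read as a shift in F0 weighting (H4, H5), and whether the location of such clusters says anything about where accent plasticity arises (H6, H7).

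**Working it through.** **1. Predicted and tested quantities.** Let H and L be mean HGA to the high-F0 and low-F0 Test stimuli, with C for Canonical and K for the comparator (Baseline or Reverse).

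- Predicted: (H_C − L_C) − (H_K − L_K).
- Tested: H_C − H_K and, separately, L_C − L_K.

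If both stimuli rise by s, each tested quantity equals s and the predicted quantity is s − s = 0. If H rises by s and L falls by s, the predicted quantity is 2s while mean response is unchanged, so there is no net enhancement. The two formulations can disagree in both directions. This step needs no assumed numbers.

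**2. The plan's own figure.** N=25 rests on behavioural effect sizes in a figure that is not shown. It cannot be reproduced, and this point does not depend on it. The documents give no neural effect size, trial count or noise SD.

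**3. Simulation.** Assumed: 30 trials per stimulus per context, AR(1) noise with rho 0.8, 40 time steps with the effect in 16, 1000 permutations, 1000 channels per scenario (Monte Carlo standard error at most √(0.25/1000) = 1.6 points). For a fair comparison, the per-stimulus column counts a channel if either test is significant at 2.5%. Ranges cover absolute and signed cluster sums.

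| True state | Either per-stimulus test | Context-by-F0 interaction |
|---|---|---|
| No change | 5-6% (unadjusted 10%) | 5% |
| Both shift 0.3 SD | 28-38% | 5% |
| Both shift 0.5 SD | 72-83% (unadjusted 84-92%) | 3% |
| 25% gain on a 2 SD response, 0.5 SD separation | 71-81% | 6% |
| Stimuli move apart, 0.5 SD each | 58-71% | 90% |
| Stimuli move apart, 0.25 SD each | 16-22% | 32% |
| One stimulus changes by 0.5 SD | 46-48% (absolute sums; unadjusted 59-61%) | 28-30% |

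In the gain row, response level rises by 0.25 × 2 = 0.5 SD and separation by 0.25 × 0.5 = 0.125 SD.

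**4. Sensitivity.** For a common 0.5 SD shift, the per-stimulus rate is 36-49% with 15 trials, 97-99% with 60 trials, 92-95% at rho 0.5 and 50-63% at rho 0.95. The interaction stays at 3-6% in all null and common-shift runs. For smaller common shifts (400 channels, 500 permutations) the per-stimulus rate is 7-8% at 0.1 SD and 12-19% at 0.2 SD. A second set-up (40 trials, 60 time steps with 20 affected, different noise, 300 permutations, 200 runs) gives, for a common 0.5 SD shift, 98% for either unadjusted test and 4.5% for the interaction.

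**5. Why power differs by pattern.** At one time step with noise SD 1, a per-stimulus contrast has standard error √(2/30) = 0.258 and the interaction √(4/30) = 0.365. If one stimulus changes by 0.5 SD, the ratios are 0.5/0.258 = 1.94 and 0.5/0.365 = 1.37, so the per-stimulus test does better. If the two move apart by 0.5 SD each, they are 1.94 and 1.0/0.365 = 2.74, so the interaction does better.

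**6. Channel selection.** Baseline Test trials would serve both to select channels and as one side of Baseline against Canonical. This was simulated with no true context change and with Test trials carrying 20% or 50% of the baseline F0 information (40,000 draws). Taking channel and F0 sign from all baseline trials biases the oriented contrast by −0.05 to −0.18 SD when the true separation is 0.3 SD. In selected channels with no true separation, two-sided error rises to 10-19%. An unoriented two-sided interaction is also affected (10-18%). With selection on non-Test trials the bias is about 0.00 SD and the error about 5%.

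**7. Sign of the cluster sum.** The threshold uses absolute t, but the SAP does not say whether summed t is signed. If one stimulus falls by 0.5 SD, its own test detects this in 57% of channels with absolute sums and 2% with signed sums.

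**The case against.** - **The contrast may be defined elsewhere.** The SAP points to a pre-registration, a grant proposal and a pilot pipeline that are not part of these documents. That limits the finding to this SAP. But the SAP describes the cluster procedure in detail, and as described it lacks the contrast.
- **Enhancement in F0-encoding channels may be shorthand for stronger F0 encoding.** Possibly, but the statistic described would still not test that, and the selection rule admits channels that encode only VOT.
- **Identical sounds compared across contexts still show context sensitivity.** True, and worth reporting. It is not evidence about F0 weighting, and H6/H7 concern plasticity of that kind.
- **The rates are conditional.** This stands. No document figure supports a common shift of any given size. The Protocol fixes the position of Baseline but reports no order effect on HGA. At 0.1 SD the excess is slight. The simulations are for single channels and do not model the multiplicity control that the SAP promises.
- **The power case is mixed.** This also stands. The per-stimulus tests win when one stimulus changes. For stimuli moving apart by 0.25 SD each, a smaller rerun gave 29% for unadjusted per-stimulus tests against 27% for the interaction. The reason to prefer the interaction is that it estimates the predicted quantity.
- **Signed sums and normalisation are points of wording.** Agreed; they need clarifying but do not carry the finding.

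**Conclusion.** The concern holds and should be fixed before the neural data are analysed. The SAP predicts a context-by-F0 contrast, tests context within each stimulus, and restates the prediction as a response level. It already has the needed structure for behaviour and for Noise, so this is an inconsistency within the plan. The mismatch itself follows from the text and simple algebra, without assumptions.

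Its practical size depends on an unknown common shift. Under the assumptions above, the chance of a significant per-stimulus cluster when differentiation has not changed runs from little above the nominal level at 0.1 SD to 72-83% at 0.5 SD, while the interaction stays near 5%. A positive per-stimulus cluster would leave the neural part of H4/H5, and the H6/H7 conclusions about accent plasticity, unsupported. The behavioural test of H5 and the Noise comparison are unaffected.

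**What to change.** 1. Reconcile the two statements of the prediction. Make differentiation the primary neural estimand, and report enhancement (the context effect on the mean of the two Test stimuli) separately as secondary.
2. Use as primary cluster statistic the two-sided interaction at each time step: the high-minus-low F0 difference in Canonical minus the same difference in Baseline or Reverse, permuting context labels within each Test stimulus.
3. Restrict this test to channels with significant baseline F0 encoding. For Baseline against Canonical, select channels (and the F0 sign, if the contrast is oriented) from baseline trials other than the Test stimuli.
4. State that clusters join time points of the same sign and that the largest absolute summed t is stored.
5. State whether HGA is normalised per block.
6. Keep the per-stimulus tests as descriptive follow-up.

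The cost is SAP wording and a few lines of code, with no new data. There are three drawbacks:

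- If only one stimulus changes by 0.5 SD, detection is 28-30%, against 46-48% for the adjusted per-stimulus tests with absolute sums.
- Selecting on non-Test trials keeps fewer channels. At a true separation of 0.3 SD it keeps 64% instead of 74% if Test trials carry 20% of the baseline F0 information, and 22% instead of 38% if they carry 50%.
- The interaction is not fully immune to multiplicative gain, which also scales the separation (0.125 SD in the gain example).

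### Baseline Test-stimulus trials help choose the channels and windows and then form one side of Baseline versus Canonical, which understates a Canonical gain in F0 differentiation where F0 encoding is weak to moderate

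*SAP*

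**What the plan says.** All the relevant text is in the SAP, mostly under Evaluating the Hypotheses: Neural Analyses.

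- **Selection.** Linear encoding models of high-gamma activity on F0 and VOT in the baseline quiet context are used to "identify the subset of electrodes and temporal windows that encode at least one of these 2 dimensions at baseline". Significance is judged by the overall regression F against a permutation null, "First, using models built on all trials".
- **Cross-validation.** This comes after selection: "goodness-of-fit will be assessed for significant models by performing leave-one-out cross-validation".
- **Comparison.** Responses to each of the two Test stimuli are compared "between Baseline vs. Canonical and Canonical vs. Reverse". The SAP notes in passing that these stimuli are cells of the F0-by-VOT grids. It then adds: "The clustering approach will look only at Baseline significant channels and time windows". Context labels are permuted on single trials inside that set.
- **Prediction (3).** Responses to the Test stimuli should separate more clearly "in the Canonical, compared to the Baseline Clear Speech context".
- **Multiplicity.** Under Rigor and Reproducibility: "Analyses will be controlled for multiple comparisons".

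No hold-out, split of trials or independent localiser is described. The Noise comparison admits a channel that is significant in either context; the Canonical comparison admits it on Baseline alone.

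**The concern.** The same Baseline Test trials serve twice: they help decide which channels and windows are examined, and they supply the Baseline side of the contrast. Canonical trials play no part in selection. Among selected channels the Baseline F0 slope is therefore too steep on average, while the Canonical response is centred on its true value. With no context effect at all, Canonical differentiation will look smaller than Baseline.

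This runs against prediction (3), which is the neural counterpart of the first half of H5 (exaggeration by Canonical input). A true gain is partly hidden, or an apparent reduction is produced. The size depends on how strongly a channel encodes F0, so the bias could also distort the H6/H7 comparison between Heschl's gyrus and higher regions if they differ in F0 encoding.

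None of the stated safeguards removes it. Leave-one-out R² is computed only for models already found significant. Shuffling context labels after selection does not repeat the selection. A stricter multiplicity threshold admits fewer channels but enlarges the bias in those it admits.

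**Working it through.** **Inputs.** The structure (two-predictor F test on all Baseline trials, Test cells inside the grid, Baseline-only restriction) is from the SAP. Grid size, trials per cell, selection threshold and encoding strength are not in the text (Figure 1a is not shown), so they are assumptions: 5x5 grid with 10 or 4 trials per cell, or 7x7 with 4; Test cells at mid VOT with extreme or next-to-extreme F0; unit noise SD; equal numbers of Canonical trials per Test stimulus. The plan gives no figure for this step to reproduce.

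**Direction, by algebra.** Let D be the Baseline mean at high-F0 Test minus that at low-F0 Test, d the F0 distance between them, and b the fitted F0 slope.

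- Cov(D, b) = σ²d/Sxx and Var(b) = σ²/Sxx, so Cov(D, b)/Var(b) = d.
- Both Test stimuli share one VOT, so D is uncorrelated with the VOT slope.
- Hence selection bias in D = d × selection bias in b. The Test cells being a small share of the grid does not dilute it.

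On a 5x5 grid with extreme-F0 Test cells, d = 4/√2 = 2.83 SD of F0.

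**Size with no true context effect.** 40,000 simulated channels per setting, selection at F p<.05. Slopes are noise SD per SD of F0. The bias is (Canonical high minus low) minus (Baseline high minus low), in noise SD.

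| F0 slope | Range, all grids | 5x5, 10 per cell, extreme F0 | 5x5, 4 per cell, extreme F0 |
|---|---|---|---|
| 0.1 | -0.10 to -0.38 | -0.19 | -0.38 |
| 0.2 | -0.03 to -0.24 | -0.06 | -0.25 |
| 0.3 | 0.00 to -0.11 | -0.005 | -0.11 |
| 0.4 | 0.00 to -0.03 | 0.00 | -0.03 |

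The columns come from separate runs, so last digits differ by simulation error (mostly 0.003 to 0.015).

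- VOT-driven channels (VOT slope 0.3 to 0.5, F0 slope 0.1), selected on F alone: +0.01 to -0.03.
- Selection at p<.001 (80,000 channels), slopes 0.2 and 0.3: -0.19 and -0.04 with 10 trials per cell; -0.52 and -0.34 with 4.
- Test cells left out of selection: within about 0.03 SD of zero throughout, which is simulation error.

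**Size with a true gain of 0.50 SD in differentiation.**

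| Setting | Observed gain, as planned | Share masked |
|---|---|---|
| slope 0.1, 10 per cell | 0.32 | (0.50-0.32)/0.50 = 36% |
| slope 0.2, 10 per cell | 0.44 | (0.50-0.44)/0.50 = 12% |
| slope 0.2, 4 per cell | 0.27 | (0.50-0.27)/0.50 = 46% |

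With the Test cells held out, the observed gain is 0.48 to 0.50.

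**The cluster test itself.** For each Test stimulus separately, as the SAP plans (5x5 grid, 40 autocorrelated windows, 200 permutations, 1,000 runs per setting, slopes 0.1 to 0.2), two-sided false positives are 4.6 to 6.8% as planned and 4.5 to 6.3% with hold-out. The high-F0 and low-F0 contrasts shift in opposite directions, but the overall rejection rate barely moves.

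**Labelling.** The SAP's closing hypothesis concerns F0-encoding channels. If strongly VOT-encoding channels (expected VOT t of 6) are labelled F0-encoding from the same Baseline t-statistics, the bias returns. With a true gain of half the Baseline difference (5x5, 10 per cell), the observed gain is -0.17 against +0.09 at an expected F0 t of 1, and +0.02 against +0.18 at 2.

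**The case against.** The strongest reply is that the error is conservative and narrow. It runs against the hypothesis, so it cannot manufacture support for it, and two-sided error stays near nominal. It touches one of three predictions, in channels of weak to moderate F0 encoding; the worst case, slope 0.1, is selected only about 13% (4 trials) to 27% (10 trials) of the time on a 5x5 grid. Its size rests on assumptions, and no calculation supports the regional distortion.

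A second reply is that the SAP tests each stimulus separately, where the gain from fixing this is small. In a simplified single-window test with a true 0.5 SD gain, correct-direction detection among selected channels was, as planned versus Test cells excluded, 6.6% versus 7.6% (slope 0.2, 10 trials), 7.7% versus 7.8% (0.3, 10), 5.5% versus 8.3% (0.1, 10) and 3.2% versus 4.8% (0.2, 4). And if enhancement in Canonical means overall amplitude rather than separation, the opposite shifts cancel: bias in the two-stimulus average was within 0.02 SD of zero.

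Most of this stands as a limit on consequence. It does not remove the problem. Prediction (3) is worded as differentiation, which is the quantity biased. A masked gain in a weakly encoding region could be read as absence of plasticity there. The same runs show detection no worse after the fix even allowing for lost channels: selected-and-detected yield is 5.4% versus 5.6% (slope 0.2, 10 trials), 1.5% versus 2.0% (0.1, 10) and 1.3% versus 1.6% (0.2, 4).

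The protocol's Study Design, item 2, has test stimuli intermixed in every block. If the sponsor intends Baseline Test trials separate from the grid trials used for selection, the SAP should say so; as written, it places them in the grid and fits all trials.

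**Conclusion.** The concern holds. The double use is explicit in the SAP, and its direction follows from algebra: Baseline F0 differentiation is inflated relative to Canonical in selected channels. Under the assumed grids and trial counts, the bias at selection p<.05 is up to about 0.4 noise SD in weakly F0-encoding channels, and it fades to near zero where selection is almost certain, through strong F0 encoding or, with F-only selection, strong VOT encoding. It masks a true Canonical gain and does not inflate two-sided false positives. Confidence is high on the mechanism and medium on the size. Canonical versus Reverse is not affected because neither side was used for selection, and N=25 does not depend on this step. It should be fixed before pre-registration, but it does not threaten the study as a whole.

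**What to change.** Add one sentence to the SAP: for Baseline versus Canonical, the encoding models that define eligible channels and windows, and any F0-encoding label, are fitted to Baseline grid trials excluding the two Test-stimulus cells, and all Baseline Test trials enter the comparison. Taking the label from the same reduced models matters: in VOT-driven channels at slope 0.1, it brings the labelling bias from about -0.20 to 0.00.

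Canonical versus Reverse may keep the all-trials selection. If both contrasts are to be reported on one set of channels, use the reduced models for both.

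The cost is a re-run of the selection model and no new data. Somewhat fewer channels qualify. At slope 0.2 and p<.05:

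| Grid | All trials | Test cells excluded | Split-half |
|---|---|---|---|
| 5x5, 10 per cell | 81% | 73-79% | about 49% |
| 5x5, 4 per cell | 41% | 35-39% | about 21% |
| 7x7, 4 per cell | 70% | 66-68% | about 39% |

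Split-half selection also removes the bias but is the weaker choice. Besides losing channels, it halves the Baseline Test trials. With 10 trials per cell the SD of the contrast rises from √(2/10 + 2/10) = 0.63 to √(2/5 + 2/10) = 0.77, about 22%.

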(**H1**) broadly, the relative perceptual weight of VOT and F0, as measured behaviorally, will be reflected in cortical response, (**H2**) with modulation as a function of baseline perceptual weights, (**H3**) shifts experimentally invoked by a change in listening context by presenting speech in noise, (**H4**) and by introducing an 'accent' that shifts short-term input regularities across VOT and F0. In the latter case, our approach will allow us to test the specific directional hypothesis (**H5**) that F0 perceptual weights in the DBSL paradigm are both exaggerated by Canonical input regularities that cleanly convey a VOTxF0 correlation consistent with English and that F0 perceptual weights are down-weighted upon introduction of a regularity that violates the typical pattern of English (supported by scalp EEG pilot, **Figure A**). Our use of sEEG allows us to evaluate these hypotheses across the supratemporal plane thereby testing the strong, and falsifiable, hypothesis (**H6**) that adaptive plasticity effects are present in HG versus (**H7**) apparent only at higher levels of the cortical hierarchy. Our ability to test these hypotheses is complemented by sEEG electrode placement in cortical regions outside STP (see **Figure 3**) which will support secondary hypotheses and serve as control electrode sites.

The study design is justified our extensive behavioral research demonstrating the feasibility of the project rationale. On the electrophysiological side, our pilot data (**Figures A,3**) demonstrate the feasibility of recording robust sEEG and EEG signals responsive to the acoustic dimensions we manipulate. This will provide clear, informative, interpretable data with which to evaluate the hypotheses listed above.

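### The SAP names electrodes outside the supratemporal plane as control sites, but its Canonical/Reverse test screens out those that encode neither F0 nor VOT at Baseline, and no step compares supratemporal with control channels

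*SAP*

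**What the plan says.** **Role of the outside-STP electrodes (SAP, Analyses).** After listing H1 to H7, the SAP adds: "Our ability to test these hypotheses is complemented by sEEG electrode placement in cortical regions outside STP", "which will support secondary hypotheses and serve as control electrode sites". It defines these sites by location only and names no analysis that uses them as controls.

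**Selection at Baseline (SAP, Evaluating the Hypotheses: Neural Analyses).** Encoding models fitted to the Baseline block are meant to "identify the subset of electrodes and temporal windows that encode at least one of these 2 dimensions at baseline". The SAP continues: "targeted analysis on this subset (described below) will then be used to compare listening contexts".

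**Canonical/Reverse contexts (same section).** The rule is repeated without exception: "The clustering approach will look only at Baseline significant channels and time windows". Responses to each Test stimulus are compared for Baseline vs. Canonical and for Canonical vs. Reverse. The null distribution comes from shuffling context labels over single trials. The prediction is restricted: "we hypothesize that HGA responses in F0-encoding channels will be enhanced in the Canonical context" relative to the other two.

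**Noise context (same section).** The rule is wider: "Encoding models will be built from the Noise context for all channels and timepoints". Comparison then follows a rule that begins "If a channel/timepoint is significant in either Baseline or Noise, the F0 and VOT coefficient", so significance in one of the two contexts is enough.

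**Conduct (Protocol).** Study Design, item 2, puts the clear-speech block first for everyone. Under Research Activities, item 1, sessions are self-paced, may spread over up to 10 days, and the research recording system is disconnected after each session.

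**The concern.** A control site is useful here because it should not show the effect under study. If it changes between blocks as the target does, the change is probably not about F0 weighting. The sites best placed to give that warning are those that encode neither acoustic dimension, and the selection rule removes them before the Canonical and Reverse contrasts are run.

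The planned test is exposed to this kind of artefact. It takes one Test stimulus at a time, so a shift common to both stimuli counts as a context difference. Context is tied to block, and Baseline is always the earliest block, so drift, fatigue or a change at reconnection can coincide with context. Shuffling labels over single trials treats trials from different blocks as exchangeable and so gives no protection against a block-level shift. The exposure is clearest for Baseline vs. Canonical. For Canonical vs. Reverse the documents do not give enough on block order to judge.

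At stake is how a positive Canonical/Reverse result (H4, H5, and its location under H6 and H7) is interpreted: as a context effect in auditory cortex, or as a recording-wide change.

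**Working it through.** No stated figure decides this point. The only sample-size figure, N=25, rests on a behavioural effect size shown in a figure and cannot be reproduced. For orientation, a paired comparison with 80% power at two-sided 0.05 implies a standardised effect of (1.960 + 0.842)/√25 = 0.56. It has no bearing on which channels are tested.

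**Step 1. Which channels enter which comparison**

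| Channel | Canonical/Reverse test | Noise comparison |
|---|---|---|
| STP, encodes F0 or VOT at Baseline | yes | yes |
| Outside STP, encodes F0 or VOT at Baseline | yes | yes |
| Any region, encodes in Noise only | no, except by chance | yes |
| Any region, encodes in neither | no, except by chance | no, except by chance |

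The rule is not regional. The excluded controls are the non-encoding ones.

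**Step 2. Chance entries.** With selection at an assumed 5% per window and W independent windows, a non-encoding channel enters with probability 1 − 0.95^W: 5% for W = 1, 23% for 5, 40% for 10, 64% for 20. Overlapping windows give less. If error is controlled per channel, entry stays near 5% and about 95% of such sites are excluded. The SAP promises multiplicity control but names no method.

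**Step 3. How often a nonspecific shift is flagged.** The documents give no trial counts, so these are assumptions. I take one time point, one Test stimulus, a two-sample t-test at two-sided 0.05, and an additive shift of s SD. This is not the full cluster procedure. The noncentrality is λ = s·√(n₁n₂/(n₁+n₂)).

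| Shift s | 60 vs. 60 trials: λ, flagged | 8 Baseline vs. 20 Canonical trials: λ, flagged |
|---|---|---|
| 0.2 | 1.10, 19% | 0.48, 7% |
| 0.4 | 2.19, 58% | 0.96, 15% |
| 0.6 | 3.29, 90% | 1.43, 28% |

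These are simply t-test power at assumed trial counts. They show that the label-shuffling logic does not guard against such a shift. They do not show that one will occur.

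**Step 4. What an unfiltered control analysis could reveal.** With K independent control channels each tested at 5%, chance positives number 0.05·K: 1.0 of 20, 2.5 of 50, 5.0 of 100. The smallest counts with an exact binomial tail of at most 0.05 are 4, 6 and 10. An additive shift of 0.6 SD reaching 20 controls would, at 60 trials per context, give about 0.90 × 20 = 18 positives. Contacts within a patient are correlated, so in practice a permutation reference is needed.

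**Step 5. What the shift does to a differentiation contrast.** Let H and L be the mean responses to the high-F0 and low-F0 Test stimuli. With a common additive shift s in Canonical, [(H + s) − (L + s)] − (H − L) = 0. A Test-stimulus by context contrast is immune to this shift. The per-stimulus comparisons in the SAP are not.

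**The case against.** The case on the other side is substantial, and much of it stands.

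- **A reader might infer that the plan depends on these controls.** It does not say so: "Our ability to test these hypotheses is complemented by sEEG electrode placement in cortical regions outside STP". They are an addition.
- **A reader might infer that control sites are never tested.** That holds only if a control means a site that encodes neither dimension. The SAP defines them by location, and an outside-STP site that encodes F0 or VOT passes the filter. Noise models cover every channel, and failure to encode is itself a regional result.
- **A reader might infer that the context effect has no possible comparator.** VOT-only channels pass the filter while the prediction concerns F0-encoding channels, so they offer a natural comparison. None is designated, however, and the SAP expects VOT encoding to change in Noise, so they are not a clean null. Encoding sites outside the STP could show genuine plasticity, so they are not one either.
- **The predictions concern differentiation between the Test stimuli**, for which a common additive shift cancels (step 5). This is correct, but the SAP specifies only per-stimulus comparisons, so the protection is implied and not written.
- **Normalisation may remove the shift.** Each subband is scaled to a baseline mean and SD. If that baseline is taken within each block, a tonic shift could vanish. The SAP does not say.
- **Filtering on a Baseline localiser is legitimate** and limits multiplicity. I agree, and the point does not ask for its removal.
- **The pre-registration or the Approach section may cover this.** Neither was available. The SAP should state it in any case.

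**Conclusion.** The point holds in a limited form. The SAP assigns a control role to outside-STP electrodes, its stated selection rule excludes those that encode neither F0 nor VOT at Baseline from the Canonical/Reverse test, and no step compares STP with control sites. A nonspecific block-level shift could therefore be flagged in STP channels without any planned analysis to expose it.

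The size is not determinable from the documents. Across the assumed trial counts and shifts in step 3 it runs from 7% to 90% of channels, and it could be near the nominal 5% if normalisation is done within blocks. The calculation also assumes that the shift is additive and reaches control sites. A gain change acting only on evoked responses need not appear where nothing is evoked.

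A reader might go further and conclude that H4 to H7 cannot be tested. The documents do not support that. H4 and H5 concern F0 weights, H6 and H7 contrast Heschl's gyrus with higher levels of the cortical hierarchy, and none is defined against non-encoding sites. What is missing is a safeguard on interpretation, worth adding before the data are analysed.

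**What to change.** In the SAP's Neural Analyses section, where shifts across listening contexts are described:

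1. Keep the Baseline-significance filter for the target channels.
2. Prespecify which outside-STP electrodes are controls, and by what criterion.
3. Add a secondary analysis that runs the same Baseline vs. Canonical and Canonical vs. Reverse cluster tests on those electrodes without the filter. Use the time windows found significant in the same patient's STP channels, since non-encoding controls have no windows of their own. Name the multiplicity method.
4. Add a within-patient STP-minus-control contrast. Interpret it as evidence against a recording-wide shift and for regional specificity. It does not prove F0 specificity: an attention effect confined to auditory cortex would also exceed the controls.
5. For F0 specificity, write in the Test-stimulus (F0) by context contrast that the differentiation predictions already imply.
6. State the trial counts per context and whether the normalisation baseline is taken within each block.

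The cost is SAP wording and extra computation on recordings already planned, with no change to N=25 or to patient procedures. The limits are that patients with few control contacts will contribute little, and that gain changes acting only on evoked responses will remain undetected by the control analysis.
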